### 8.5.1 Adverse Events of Interest (Part B [REDACTED])

Adverse events of interest (AEIs) are AEs for a particular product or class of products that a Sponsor may wish to monitor carefully. AEIs may be serious or nonserious. Such events may require further investigation to better characterize and understand them. In the BMS-986165 clinical development program, certain skin-related AEs (eg, acne) and infection AEs have been identified as potential AEIs; however, there has been no definitive assessment on the causal relationship between these events and treatment with BMS-986165. Therefore, additional information about certain AEs, may be collected on the case report form in order to better characterize and understand them. Therefore, if an AE term corresponding to any of these categories is entered, the user will be prompted by the electronic data capture (EDC) system to enter additional information on the eCRF.

### 8.5.2 Time Period and Frequency for Collecting Information About Adverse Events and Serious Adverse Events

The collection of nonserious AE information will begin at the first dose of MMF in Part A and will continue until the final study visit. The Reference Safety Information in Sections 5.6.1 and 5.6.2 of the IB should be used to determine the expectedness of SAEs for expedited reporting.

All SAEs, including those thought to be associated with protocol-specified procedures must be collected from the time the ICF is signed through 30 days after the final dose of any study treatment. Any SAEs that begin after 30 days after the final dose of study treatment must be reported if assessed as related to the study treatment or any protocol-specified procedure.

Medical occurrences that begin after obtaining informed consent but before the first dose of MMF in Part A will be recorded as medical history on the appropriate section of the eCRF module.

All SAEs will be recorded and reported to the Sponsor or designee within 24 hours after the investigator or designee becomes aware of the event. The investigator will submit any updated SAE data to the Sponsor or designee within 24 hours of learning of the information.

Investigators are not obligated to actively seek AEs or SAEs in former study subjects beyond 30 days after the final dose of any study treatment. However, if the investigator learns of an SAE (including a fatal SAE) after that time and believes the event to be reasonably related to the study treatment or study participation, the investigator must promptly notify the Sponsor.

The method of evaluating and assessing causality of AEs and SAEs and the procedures for completing and reporting/transmitting SAE reports is provided in [APPENDIX 3](#).

### **8.5.3 Method of Detecting Adverse Events and Serious Adverse Events**

Adverse events may be spontaneously reported by subjects or may be elicited during open-ended questioning, examination, or evaluation of a subject. To prevent reporting bias, investigators should avoid asking subjects about specific AE terms.

### **8.5.4 Follow-up of Adverse Events and Serious Adverse Events**

Nonserious AEs should be followed until the event resolves, stabilizes, or is reported as an SAE (see [APPENDIX 3](#)).

Follow-up is also required for AEs and SAEs that cause interruption or discontinuation of study treatment and for those present at the end of study treatment, as appropriate.

Nonserious AEs must be recorded and described on the nonserious AE page of the eCRF. Completion of supplemental eCRFs may be requested for AEs such as skin reactions, infections, and/or laboratory abnormalities that are reported/identified during the course of the study.

After the initial AE or SAE report (all subjects), investigators are required to proactively follow each subject at subsequent visits/contacts.

All subjects with SAEs and randomized subjects with AEs will be followed until the event is resolved or resolved with sequelae, until the condition stabilizes or is otherwise explained, or until the subject is determined to be lost to follow-up (as defined in [Section 7.5](#)).

Further information on follow-up procedures is given in [APPENDIX 3](#).

### **8.5.5 Regulatory Reporting Requirements for Serious Adverse Events**

The investigator must promptly report SAEs to the Sponsor so that legal and ethical obligations are met regarding the safety of subjects and the accuracy and completeness of the safety profile of BMS-986165.

If investigators receive SAE reports or other specific safety information (eg, a safety summary or listing of SAEs) from the Sponsor, the site staff will file the documents with the Investigator's Brochure and will notify the Institutional Review Board (IRB)/Independent Ethics Committee (IEC), if appropriate, according to local requirements.

The Sponsor or designee will be reporting suspected, unexpected serious adverse reactions to the appropriate regulatory authorities and IRBs/IECs according to applicable local and global guidelines and laws, including European Directive 2001/20/EC and Food and Drug Administration Code of Federal Regulations (CFR) 21 Parts 312 and 320.

### **8.5.6 Pregnancy**

In the event a subject becomes pregnant during the trial, the study treatment must be discontinued immediately. If the subject becomes pregnant while on treatment or within 3 days of discontinuing study treatment, the investigator must immediately notify [REDACTED] Drug Safety of this event and complete and forward a Pregnancy Surveillance Form to [REDACTED] Drug Safety within 24 hours of awareness of the event in accordance with SAE reporting procedures described in [APPENDIX 3](#). The investigator must also notify the medical monitor or designee of this event within 24 hours of awareness of the pregnancy.

Follow-up information regarding the course of the pregnancy, including perinatal and neonatal outcome and, where applicable, offspring information must be reported on the Pregnancy Surveillance Form. Investigators will continue to follow-up with subjects who are discontinued from study treatment early because of pregnancy, and will submit additional information on the Pregnancy Surveillance Form regarding the course of the pregnancy, including perinatal and neonatal outcomes.

Any pregnancy that occurs in a female partner of a male subject should be reported to [REDACTED] Drug Safety. For the Sponsor or designee to collect any pregnancy surveillance information from the female partner, the female partner must sign an ICF for disclosure of this information. Information on this pregnancy will be collected on the Pregnancy Surveillance Form.

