**Table 3: Procedures and Assessments in Part B of IM011073 (52-Week Blinded Treatment Period)**

[figure not shown]
Visit Number	B1	B2	B3	B4	B5	B6	B7	B8	B9	B10	B11	B12	B13	B14/ EOT a	B15 a	Notes
Study Week/Day	D1	W4 D29 ±3d	W8 D57 ±3d	W12 D85 ±3d	W16 D113 ±3d	W20 D141 ±3d	W24 D169 ±3d	W28 D197 ±3d	W32 D225 ±3d	W36 D253 ±3d	W40 D281 ±3d	W44 D309 ±3d	W48 D337 ±3d	W52 D365 ±3d	28-D FU ±3d	The final study visit (for noncontinuing subjects) will occur 28d±3d after the visit at W52
Laboratory tests and other procedures																
UA with microscopic examination		X	X	X	X	X	X	X	X	X	X	X	X	X	X	Clean-catch specimen; if the UA is positive for leukocytes, blood, or bacteria, a urine culture should be performed if appropriate
UPCR		X	X	X	X	X	X	X	X	X	X	X	X	X		First morning voided specimen; second morning void may be used if first morning void was not collected
24-hour urine for UPCR c							X and ±7d							X and ±7d		Two 24-hour urine specimens will be collected for Visits B7 and B14; one should be collected at the visit and one returned either before or after per site/subject preference. The subject must provide both samples within the total 14-day window.
Urine pregnancy test for WOCBP only	X	X	X	X	X	X	X	X	X	X	X	X	X	X	X	A negative result within 24 hours before dosing on D1 is required

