## **6.3 Treatments Administered**

### **6.3.1 Open-label Mycophenolate Mofetil – All Subjects**

Open-label MMF will be dispensed to all subjects in Part A, Part B [REDACTED].

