## **7 DISCONTINUATION CRITERIA**

### **7.1 Discontinuation from Study Treatment**

Subjects **MUST** discontinue the IP (and non-IP at the discretion of the investigator) for any of the following reasons:

- A subject requests to stop study treatment; these subjects will remain in the study and must continue to be followed for protocol-specified follow-up procedures, unless the subject specifically withdraws consent for any further contact with him/her or persons previously authorized by the subject to provide this information
- Any clinical AE, laboratory abnormality, or intercurrent illness that, in the opinion of the investigator, indicates that continued participation in the study is not in the best interest of the subject
- Termination of the study or the program by BMS
- Loss of ability to provide consent through imprisonment or involuntary incarceration for treatment of either a psychiatric or physical (eg, infectious disease) illness

In the case of pregnancy, all study treatment must be stopped immediately. The investigator must immediately notify the [REDACTED] medical monitor or designee of this event (no later than 24 hours after becoming aware of the pregnancy). See [Section 8.5.6](#) for more information about pregnancy.

Unless they withdraw consent for further follow-up procedures or lose the ability to consent freely (eg, through imprisonment or involuntary incarceration for treatment of psychiatric or physical illness), subjects who discontinue from the study treatment early should still attend the final

end-of-treatment visit and the 28-day follow-up visit. They will also be followed for SAEs for 30 days after the final dose of IP, and will be evaluated on a case-by-case basis regarding the optional end-of-treatment renal biopsy.

If study treatment is discontinued prior to the subject's completion of the study, the reason for the discontinuation must be documented in the subject's medical records and entered on the appropriate eCRF page.

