### Reporting of SAEs to Sponsor or Designee

SAEs, whether related or not related to study drug, and pregnancies must be reported to [REDACTED] Drug Safety within 24 hours of awareness of the event.

SAEs must be recorded on the SAE Report Form. For studies capturing SAEs through electronic data capture (EDC), electronic submission is the required method for reporting. In the event the electronic system is unavailable for transmission, paper forms must be used and submitted immediately. When paper forms are used, the original paper forms are to remain on site.

Pregnancies must be recorded on a paper Pregnancy Surveillance Form and transmitted via email or confirmed facsimile (fax) transmission to:

**SAE Email Address:** [REDACTED]

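### Section 8.5.6 requires reporting of a subject's pregnancy only if it begins on treatment or within 3 days of stopping; this makes no allowance for MMF's 6-week post-dose period and contradicts Appendix 3

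*Combined protocol and SAP*

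**What the plan says.** Section 8.5.6 sets the condition under which the investigator must notify Drug Safety and send a Pregnancy Surveillance Form within 24 hours: "If the subject becomes pregnant while on treatment or within 3 days of discontinuing study treatment". The same sentence points to Appendix 3 for the procedure. Later in the section, pregnancies in the partners of male subjects are to be reported with no time condition.

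Appendix 3, under Reporting of SAEs to Sponsor or Designee, is worded differently. It says "SAEs, whether related or not related to study drug, and pregnancies must be reported to" Drug Safety within 24 hours of awareness, and "Pregnancies must be recorded on a paper Pregnancy Surveillance Form and transmitted via email or confirmed facsimile (fax) transmission to" the address given. Neither sentence has a post-dose limit. Elsewhere, Appendix 3 refers the reader to 8.5.6 for reporting pregnancies. Appendix 4, under Collection of Pregnancy Information, refers to both 8.5.6 and Appendix 3.

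On the drugs themselves, Section 6.3.1 says "Open-label MMF will be dispensed to all subjects in Part A, Part B". Table 5 and Section 6.8 class MMF as investigational product, and the definition of study treatment in Section 6 covers marketed products. Appendix 4 builds the BMS-986165 contraception period from five half-lives (3 days) plus 30 days for an ovulatory cycle. It then says that the longer MMF requirement, at least 6 weeks after the last dose, is the one that applies. Inclusion criterion 4.d repeats the 6 weeks.

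**The concern.** The protocol uses the longer MMF period to prevent pregnancies, but the figure that triggers reporting of one matches only BMS-986165. Every subject takes MMF. In Part A, and in Part B for subjects who are not randomized, MMF is the only study drug, so for them five half-lives of BMS-986165 has no bearing on exposure.

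The two reporting rules also disagree, and the documents do not say which prevails. The narrower rule sits in the section titled Pregnancy, to which both appendices refer, so a site could reasonably take it as the operative one. At stake is the completeness of pregnancy reports in a trial whose background drug carries its own post-dose contraception requirement. A pregnancy that does not meet the 8.5.6 condition might never reach Drug Safety or have a form opened.

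**Working it through.** This is mainly a comparison of texts, with a little arithmetic to place the limits on one time line. Day 0 is the last dose of MMF, with blinded treatment (if any) stopped no later than that.

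**Inputs**
- Reporting limit in 8.5.6: 3 days after discontinuing study treatment. It refers to when the subject becomes pregnant, not to when the site finds out.
- BMS-986165 (Appendix 4): five half-lives = 3 days, ovulatory-cycle allowance = 30 days.
- MMF (Appendix 4 and inclusion criterion 4.d): at least 6 weeks.
- Appendix 3: report within 24 hours of awareness, no post-dose limit.

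**Reproducing the plan's own figure**
- BMS-986165 contraception period: 3 + 30 = 33 days, as stated in Appendix 4. The 3-day component has the same length as the 8.5.6 limit. No other 3-day figure for either drug is explained. That the limit was taken from this component is an inference, because 8.5.6 gives no reason for it.

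**MMF period in days**
- 6 weeks × 7 = 42 days, as a minimum.

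**The two rules side by side, by time of conception**

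| Conception | 8.5.6 read alone | Appendix 3 | Within the MMF contraception period? |
|---|---|---|---|
| On treatment | Report | Report | Yes |
| Days 1 to 3 | Report | Report | Yes |
| Days 4 to 42 | Not required | Report | Yes |
| After day 42 | Not required | Report | No (42 days is the minimum) |

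The rules agree in the first two rows and differ in the last two. The third row matters most: the protocol still requires contraception because of MMF, while 8.5.6 no longer requires a report.

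**Consistency within 8.5.6**
- Partner pregnancies carry no time limit. Partners, who receive no study drug, are therefore covered more broadly than subjects who do.

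**The case against.** The strongest reply is that 8.5.6 sends the site to Appendix 3 in the same sentence, and Appendix 3 requires pregnancies to be reported without limit. A site that follows both would miss nothing. There are backstops too: a congenital anomaly is an SAE, and SAEs judged related must be reported even after the 30-day window. This stands, and it rules out calling the clause a complete surveillance gap. It does not remove the contradiction. The pointer to Appendix 3 concerns procedure and comes after the 3-day condition has already restricted the duty, and Appendix 3 points back.

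A second reply is that a limit of five half-lives of the investigational drug is a legitimate exposure-based choice. For BMS-986165 alone that may be so. The section gives no such reason, however, and the choice does not explain why Appendix 3 omits the limit.

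Several stronger readings are tempting but not supported:

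- **A conflict with Section 7.1.** That section requires notice to the "medical monitor or designee of this event (no later than 24 hours after becoming aware of the pregnancy") and has no 3-day condition. But it deals with stopping treatment in a subject who is pregnant, covers the medical monitor rather than Drug Safety or the form, and defers to 8.5.6.
- **MMF is ignored altogether.** It is not. The 3 days run from stopping study treatment, which includes MMF, so a subject still taking MMF counts as on treatment. What is missing is any allowance for MMF's longer post-dose period.
- **The difference between 3 days and another window measures the shortfall.** A contraception period is not a reporting window, and the BMS-986165 period contains an ovulatory-cycle allowance. The documents give neither an MMF half-life nor a breakdown of the 6 weeks. The SAE window, under which events "must be collected from the time the ICF is signed through 30 days after the final dose of any study treatment", is no benchmark either, because Appendix 3 ties pregnancies to SAE transmission timing and processes, not to the SAE collection period.
- **The follow-up visit shows the size of the problem.** Table 3 schedules the "Urine pregnancy test for WOCBP only" at Visit B15, and "The final study visit (for noncontinuing subjects) will occur 28d±3d after the visit at W52". A positive test there can reflect conception on treatment or within 3 days, which 8.5.6 already covers. Setting a detection date against a conception limit shows nothing about how many cases would be exempt.

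**Conclusion.** The point holds as an internal contradiction with a risk of under-reporting. Read alone, 8.5.6 does not require a report of a subject pregnancy conceived from day 4 to day 42 after the last MMF dose; Appendix 3 does. A site relying only on 8.5.6 could leave such a case unreported, while a site following Appendix 3 would report it.

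The 42 days rest on the stated 6-week minimum and on the last MMF dose ending study treatment. They mark where the two rules part within the period for which contraception is required; they do not estimate MMF exposure, and the documents give no figure from which the number of pregnancies affected could be estimated. No endpoint or efficacy analysis is affected.

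**What to change.** In Section 8.5.6, cut the clause "If the subject becomes pregnant while on treatment or within 3 days of discontinuing study treatment" back to its opening words, so that the only condition is that a subject becomes pregnant. Any subject pregnancy that the site becomes aware of is then reported within 24 hours and recorded on the form, as Appendix 3 already requires. Appendix 3 needs no change.

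If the sponsor prefers to keep a window, it should run at least 6 weeks after the last dose of MMF or of blinded study treatment, whichever is later. Appendix 3 should then state the same window, so that the two places agree.

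The cost is one clause and a few more pregnancy reports. No visit or test is added. Pregnancies arising after the final visit would come to light only if the subject tells the site.

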### **8.5.7 Laboratory Test Result Abnormalities**

The following laboratory test result abnormalities should be captured on the AE eCRF page:

- A laboratory test result that is deemed clinically significant or meets the definition of an AE (if applicable) or SAE
- A laboratory test result abnormality that leads to interruption of or early discontinuation from the blinded study treatment
- A laboratory test result abnormality that requires specific corrective therapy

If a laboratory test result meets the definition of an AE (if applicable) or SAE, the laboratory test result should be reported as an AE or SAE and submitted to [REDACTED] Drug Safety as specified in [APPENDIX 3](#).

It is expected that wherever possible, the clinical rather than laboratory term would be used by the reporting investigator (eg, anemia versus low hemoglobin value).

### **8.5.8 Potential Drug-induced Liver Injury**

Whenever possible, liver-related laboratory abnormalities should be confirmed in a timely manner before a potential drug-induced liver injury (DILI) event is reported. All potential DILIs (defined

as meeting all the criteria below) must be reported as SAEs (see [APPENDIX 3](#) for reporting details):

- Transaminase (ALT or AST) elevation  $> 3 \times$  ULN
- Total bilirubin  $> 2 \times$  ULN, without initial findings of cholestasis (elevated serum alkaline phosphatase [ALP])
- No other immediately apparent possible causes of AST or ALT elevation and hyperbilirubinemia, including, but not limited to, viral hepatitis, pre-existing chronic or acute liver disease, or the administration of other drug(s) known to be hepatotoxic

### **8.5.9 Other Safety Considerations**

Any significant worsening noted during interim or final physical examinations, electrocardiogram, x-ray filming, any other potential safety assessment required or not required by protocol should also be recorded as an AE or SAE, as appropriate, and reported accordingly.

### **8.6 Overdose**

For this study, any dose of BMS-986165 greater than 24 mg within a 24-hour time period will be considered an overdose. However, if a subject takes a higher dose than assigned (even if less than 24 mg in a 24-hour period), this deviation should be documented appropriately.

In the event of an overdose, the investigator should carry out all of the following actions:

1. Contact the [REDACTED] medical monitor immediately
2. Closely monitor the subject for AEs, SAEs, and laboratory abnormalities until BMS-986165 can no longer be detected systemically (at least 3 days)
3. [REDACTED]
4. Document the quantity of the excess dose as well as the duration of the overdosing in the eCRF

### **8.7 Safety**

Planned time points for all safety assessments are listed in the Schedule of Activities ([Section 1.3](#)). All urgent safety concerns must be discussed with the Sponsor immediately upon occurrence or awareness to determine if the subject should continue or discontinue treatment. Only data from protocol-specified procedures and assessments should be submitted on eCRFs. Additional assessments may be performed as part of standard of care, and these data should remain in the subject's medical record but should not be reported on eCRFs.

Safety evaluations in addition to AE monitoring are physical examination ([Section 8.7.1](#)), TB screening ([Section 8.7.2](#)), vital signs, ECGs, concomitant medication use, and clinical laboratory test results ([Section 8.7.3.2](#)).

Planned time points for all safety assessments are listed in the Schedule of Activities.

### **8.7.1 Physical Examinations**

Schedules for physical examinations are provided in [Section 1.3](#). Worsening of lupus or lupus nephritis should be reported in the physical examination as lupus related and on the lupus/lupus nephritis disease assessments.

All physical examinations will be complete examinations and may be performed by a Doctor of Medicine (MD), or someone who is authorized and trained to perform the examinations and has been delegated this task by the Principal Investigator. Although not required, every effort should be made to ensure the same evaluator will complete the examination for each subject at all visits throughout the study. The identity of the examiner is to be recorded in the source notes.

### **8.7.2 Tuberculosis Screening and Chest Imaging**

A physical examination will be performed during screening to assess a subject's eligibility. If available, results of an x-ray or CT scan of the chest from no more than 6 months before screening may be used. Prospective subjects who meet all other eligibility criteria but do not have chest x-ray or CT results within the previous 6 months will need to have a chest x-ray performed as part of screening for TB. A subject must not have active signs or symptoms of TB, as judged by the investigator, to be eligible for the study.

[figure not shown]
In addition to a complete physical examination and medical history to evaluate exposure to TB, all subjects will have a screening IGRA, eg, T-spot®, QuantiFERON®-TB Gold, or QuantiFERON®-TB Gold Plus performed at the central laboratory. A subject with an indeterminate IGRA result at screening must be retested for confirmation; the second test may be performed locally after consultation with the [REDACTED] medical monitor. If the second result is again indeterminate, the TB questionnaire ([APPENDIX 20](#)) will be completed. If this TB questionnaire indicates no new/recent risks, then the subject may be eligible provided no other exclusion criterion for TB is met and ongoing IGRA testing will occur every 6 months. If the TB questionnaire indicates new/recent risks, the subject will be excluded from the study. If the second result is positive, the subject should be treated as having LTBI, provided there are no signs or symptoms of active TB. If the second result is negative, the subject may be eligible to participate in the study, provided no other exclusion criterion for TB is met.

For the subjects with two indeterminate IGRA results at screening who have no new/recent risks per the TB questionnaire, re-evaluation every 6 months with the TB questionnaire and repeat IGRA will be performed:

[figure not shown]
- If no new risks are identified and IGRA remains indeterminate, continue re-evaluation every 6 months.
- If new risks are identified and IGRA remains indeterminate, investigator will discuss with medical monitor to determine next action based on risks.

- If IGRA is newly negative, then ongoing IGRA testing may be discontinued.
- If IGRA is newly positive, then IP must be held and subject evaluated for active TB. If chest x-ray shows no evidence of active TB and there are no symptoms/signs of active TB, then subject must initiate prophylactic treatment for LTBI per local guidelines. IP will be held until subject has been on prophylaxis treatment for 30 days.

